6.4 Safety

All subjects receiving any amount of study drug will be included in the safety analysis. Laboratory findings, adverse events, concomitant medications, and medical history data will be provided in subject listings.

Laboratory values, incidence of high or low abnormal values, changes from baseline (Baseline value is the last value before the first study drug infusion.) will be summarized. Vital signs will be summarized. Individual listings of AEs [including AEs as reported, start, duration, severity, relation to study drug] will be provided. The incidence of treatment-emergent AEs will be summarized using the Medical Dictionary for Regulatory Affairs (MedDRA). AEs with a start date prior to first infusion or more than 3 days after the last infusion are not treatment emergent. Treatment emergent determination will be derived after missing or incomplete AE start date is imputed. Imputation rules for missing and incomplete AE start are described in Section 4.3

Two laboratory analytes, Anti HSP70 and Anti BHK, will be summarized in a listing that will include all values for those subjects with any positive result. Incidence of HSP-70 antibody formation and hamster protein antibody formation will be assessed from these laboratory tests.

Inhibitor development, as measured by Bethesda assay, as well as the results from all ELISA assays, will be summarized by preparation and timepoint and presented in subject listings. The frequency of subjects who develop positive inhibitor titers (Bethesda ≥ 0.6 BU) will be presented.

Vital signs and change from baseline of vital signs will be summarized with descriptive statistics distinguishing pre-infusion and post-infusion readings. Baseline is the last measurement before the first study drug infusion. Post-infusion minus pre-infusion values will be summarized at Month 1, Month 2, and final visit in the main study.

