- Blood sample for the determination of recovery to be taken at 20-30 min after end of *infusion*. (as of Amd 1) (*Only for subjects who start prophylaxis at Baseline, for others, recovery should be done when prophylaxis is started [as of Amd 6].*)
- *Optional PK: Additional blood samples at 4 h and 24 h post infusion (can also be performed at a later visit; obtained only once during study.)*
Note to investigators: In compliance with European Medicines Agency (EMA) guidance and for subject safety, no more than 1% blood volume may be obtained at any one visit, and no more than 3% may be taken in one month (see Section 14.4). If additional PK samples are taken, the total volume of blood drawn in 24 h will be too high for infants weighing less than 9 kg, who must therefore be excluded from the PK sub-study. (as of Amd 1, Amd 3)
- *Recommended (as of Amd 7) pharmacogenetics in PUPs/MTPs (Part B and extension): collect blood sample for biomarker investigation – requires signed informed consent. This blood draw will be done once only, and can be performed at any visit except Screening, ideally at Visit 3 or whenever the subject’s body weight/condition is suitable for an additional blood draw (as of Amds 4 and 6). Additional informed consent is required. (as of Amd 7)*
- Documentation of AEs
- Check of *understanding of EPD use*. *Repeat training on the device if required. (as of Amd 1)*
- Instruction on the prophylaxis regimen to be administered to the subject

Begin regular weekly contact between parents and the *site* to check the EPD documentation until next clinic visit. *Contacts should be documented in the medical record. (as of Amd 1)*

7.1.2.3 Visit 3 – Month 1 for Part A; ED ~5 (4 ED +/- 1) for Part B (as of Amd 1)

The following procedures and assessments will be performed:

- Check of EPD *entries* and bleeding history. *Collect information on AEs, update of concomitant medication and completion of Healthcare Resources Utilization Questionnaire. (Appendix 14.3). (as of Amd 1 and Amd 3)*
- Measurement of body height/*length* (as of Amd 1) and weight
- *Measurement of vital signs: Systolic and diastolic blood pressure, heart rate, and body temperature. (Blood pressure may be deferred if appropriate cuff size or equipment is not available). (as of Amd 1)*
- *Blood sample for inhibitor testing and determination of FVIII:C trough levels (≥ 48 h after last FVIII treatment). (as of Amd 1)*
- *Infusion of study drug (Part A only) (as of Amd 1)*

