 - **Serum chemistry (sodium [Na], potassium [K], bicarbonate [CO], chloride [Cl], creatinine, alanine and aspartate aminotransferases [ALT, AST], total bilirubin. (See Section 14.4 for children <10 kg) (as of Amd 1)**
- Blood sample for inhibitor testing and determination of FVIII:C trough levels (≥ 48 h after last FVIII **treatment**). (as of Amd 1)
- HSP-70 antibodies (**in children > 7 kg**). (as of Amd 1)
- **Infusion** of study drug. (as of Amd 1)
- **Vital signs after infusion**. (as of Amd 1)
- Blood sample for the determination of recovery to be taken at 20-30 min after end of **infusion**. (as of Amd 1)
- **Optional PK: Additional blood samples at 4 h and 24 h post infusion, for Part B subjects also at 20-30 min after end of infusion (can also be performed at a later visit; obtained only once during study.)**
Note to investigators: In compliance with EMA guidance and for subject safety, no more than 1% blood volume may be obtained at any one visit, and no more than 3% may be taken in one month (see Section 14.4). If additional PK samples are taken, the total volume of blood drawn in 24 h will be too high for infants weighing less than 9 kg, who must therefore be excluded from the PK sub-study. (as of Amd 1, Amd 3)
- **Recommended (as of Amd 7) pharmacogenetics in PUPs/MTPs (Part B and extension): collect blood sample for biomarker investigation, if not taken previously – requires signed informed consent. This blood draw will be done once only, and can be performed at any visit except Screening (as of Amds 4 and 6)**
- Check of EPD **entries** of interval treatment and bleeding history.

For subjects not participating in the optional extension study:

- Return of EPD
- Return of used and unused study **vials (as of Amd 1)** for final drug accountability

- **Follow-up phone call (1-2 weeks after end of treatment)**
Call parents/caregiver via telephone and review any new AEs and changes in concomitant medication since the last study visit.

For subjects participating in the optional extension study:

- Informed consent signed by parents/legal representative must be available.
- Continuation of prophylaxis treatment
- **Begin** regular **monthly** contacts between parents and the **site** to check the EPD documentation until next clinic visit. *(as of Amd 1)*

7.1.2.9 Extension study visits – 6 months after completion of Part A or B; then every 6 months (as of Amd 1)

The following procedures and assessments will be performed:

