- The admission results in a hospital stay of less than 12 hours
- The admission is pre-planned
(i.e. elective or scheduled surgery arranged prior to the start of the study)
- The admission is not associated with an AE
(eg, social hospitalization for purposes of respite care).

However, it should be noted that invasive treatment during any hospitalization may fulfill the criterion of ‘medically important’ and as such may be reportable as an SAE dependent on clinical judgment. In addition, where local regulatory authorities specifically require a more stringent definition, the local regulation takes precedence.

- d. Results in persistent or significant disability / incapacity

Disability means a substantial disruption of a person’s ability to conduct normal life’s functions.

- e. Is a congenital anomaly / birth defect
- f. Is another medically important serious event as judged by the investigator.

Note: Any inhibitor development is considered an SAE.

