6.4.1 Adverse events

The investigator has to record on the respective CRF pages all adverse events occurring in the period between the signing of the informed consent form and the end of the follow-up phase. The original terms used by investigators to report AEs via the CRFs will be coded using the Medical Dictionary for Regulatory Activities (MedDRA).

For each AE, the number and percentage of subjects who experienced at least 1 occurrence of the given event will be tabulated according to the affected primary system organ class (SOC) and preferred term (PT) by dose cohort and dose actually received. A total column will be included in all safety summaries.

Frequency tables, showing an overall summary of number of subjects with drug-related AEs, SAEs and AESIs will be given, and will include the following information:

- maximum intensity for any AE,
- AE related deaths,
- AE resulting in permanent discontinuation of study drug,
- treatment emergent AE.

AEs will be considered treatment-emergent if they begin after the first administration of study drug and they do not start after more than 7 days after the last administration. Determination of whether or not an event is treatment-emergent will be derived after the missing or incomplete AE start date is imputed. In case an adverse event starts on the day of first administration of study drug and the time of onset is not known, the event is considered to be not treatment emergent, if it is reported to occur before the first dose of study drug. In all other cases the event is considered to be treatment emergent. Inhibitors will be defined as treatment-emergent if they develop after first study drug application. Imputation rules for missing and incomplete AE start are described in section 4.3.

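### Part A closes the treatment-emergent window 3 days after the last infusion with no exception for inhibitors, while Part B allows 7 days and exempts them, so Part A's treatment-emergent AE table can omit an inhibitor SAE

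*SAP*

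**What the plan says.** **Part A SAP, Section 6.4.** The incidence of treatment-emergent AEs is summarized under this rule: "AEs with a start date prior to first infusion or more than 3 days after the last infusion are not treatment emergent". No separate rule is given for inhibitors. The supplement of 18 Jul 2013 revises only Sections 4.1, 4.4 and 6.2, so the 3-day limit stands. The same section also plans a summary of inhibitor results by timepoint, the frequency of subjects with titers of 0.6 BU or more, and listings of AEs and inhibitor results. None of these is tied to the treatment-emergent window.

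**Part B SAP, Section 6.4.1.** Events qualify if they begin after the first administration and "they do not start after more than 7 days after the last administration". It then adds: "Inhibitors will be defined as treatment-emergent if they develop after first study drug application". AEs are to be recorded "between the signing of the informed consent form and the end of the follow-up phase".

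**Protocol.** Section 7.5.1.1 notes: "Any inhibitor development is considered an SAE". Section 7.1.2.8 schedules a telephone call 1 to 2 weeks after the end of treatment, for children not entering the extension, to "review any new AEs and changes in concomitant medication since the last study visit". Section 7.1.2.10 schedules a similar call after the extension. Section 8.5 plans an additional analysis of all main-study and extension data.

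**The concern.** One protocol and one drug have two cut-offs, and neither SAP gives a reason for the difference. The event most exposed is the one that matters most for the safety of a factor VIII product. An inhibitor is a laboratory finding. It is recognised when a sample is drawn at least 48 h after a dose, tested centrally and then confirmed, so its recorded onset can fall days after the last infusion in a child who has stopped. Part B deals with this by exempting inhibitors from the window; Part A does not.

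Safety is half of the primary objective. A Part A report could show an inhibitor in its titer frequency that its treatment-emergent AE table does not contain. When Part A, Part B and the extensions are brought together in the overall analysis, treatment-emergent rates for previously treated children and for PUPs/MTPs would follow different counting rules.

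**Working it through.** The documents give no figure to reproduce. The check is a comparison of the rules, with day-count arithmetic.

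**Inputs**
- Part A window after the last infusion: 3 days (Part A SAP 6.4).
- Part B window: 7 days, with no upper limit for inhibitors (Part B SAP 6.4.1).
- Post-treatment AE review for children not entering the extension: day 7 to day 14 (Protocol 7.1.2.8).
- Planned Part A size: 50 (Protocol 8.6).

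**Share of post-treatment collection time counted** = window / day of call

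| | Call at day 7 | Call at day 14 |
|---|---|---|
| Part A | 3/7 = 43% | 3/14 = 21% |
| Part B | 7/7 = 100% | 7/14 = 50% |

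**Days collected but outside the window** = day of call minus window
- Part A: 7 − 3 = 4 to 14 − 3 = 11 days.
- Part B: 7 − 7 = 0 to 14 − 7 = 7 days, with inhibitors exempt.

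**How an inhibitor AE would be flagged in Part A**
1. *Found at the final visit, including early termination, and dated to that sample.* Section 7.1.2.8 lists the inhibitor sample before an infusion of study drug at the same visit. The onset precedes the last infusion, so the event is treatment-emergent.
2. *Dated to the confirmatory sample.* Section 14.5 requires pre- and post-infusion samples for confirmation. If that infusion is study drug, the last-infusion date moves forward and the event is treatment-emergent.
3. *Child continues on study drug, for example as immune tolerance induction (Sections 4 and 6.1.5).* Infusions go on, so the window has not closed.
4. *Child has no further study infusion and is first sampled more than 3 days after the last one.* Not treatment-emergent in Part A; treatment-emergent under the Part B rule.
5. *No further study infusion, and the AE is dated to receipt of the result more than 3 days after the last one.* Not treatment-emergent in Part A; treatment-emergent under the Part B rule.

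Routes 4 and 5 are the gap. Neither SAP says which date starts an inhibitor AE, so route 5 depends on the habit of whoever completes the form.

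**Hypothetical effect of one such case among 50 children.** The treatment-emergent figure would be 0/50 (exact 95% CI 0 to 7.1%) in place of 1/50 = 2% (0.05 to 10.6%). The documents do not show that such a case occurred.

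**The case against.** The strongest reply is that the practical effect is small. A reader might infer that Part A loses an inhibitor SAE altogether. It does not: the titer frequency and the listings carry it regardless of the window, and Section 8.3 of the protocol separately requires an inhibitor rate. Section 6.4 of the Part A SAP names a treatment-emergent AE incidence summary but no treatment-emergent SAE table, so what is at risk is an entry in an AE table. Routes 1 to 3 above are closed or largely closed. All of this stands, and it confines the gap to routes 4 and 5.

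A reader might also infer that late events are discarded under both rules, using 21% and 50% as fixed figures. Those assume a call at day 14. With a call at day 7, Part B loses nothing, and AEs outside the window are still listed.

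A third tempting inference is that only 24 h (48 to 72 h after the last dose) remains for a countable inhibitor sample in a child who has stopped. The Part A rule is worded by start date, so a calendar-day reading could extend this to nearly 48 h. Nothing in the documents shows that a child in whom treatment is failing would be sampled late. Section 14.5 asks for immediate notification of the sponsor and blood tests when an inhibitor is suspected.

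Finally, the protocol sets no treatment-emergent cut-off, Parts A and B are to be summarized separately, and Part A has already been reported. The SAP for the overall analysis, the TLF specifications and the Analysis Datasets documents are not among those supplied, so they may already deal with the point. These arguments show that neither window length is an error in itself. They do not explain why inhibitors are exempt in one part only.

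**Conclusion.** The point holds in a limited form. The treatment-emergent definitions differ between parts (3 days against 7, with an inhibitor exemption in Part B only). As a result, Part A's treatment-emergent AE incidence table can omit an inhibitor SAE that the titer frequency and the listings still show. This requires that the child receives no further study infusion and is sampled, or has the AE dated, more than 3 days after the last one.

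For AEs in general, Part A counts 21-43% of the post-treatment collection time and Part B 50-100%. These figures assume that collection ends with a call at day 7 to 14, and they apply to children who do not enter the extension. The number of events affected cannot be known from the documents and may be zero. This is an inconsistency worth correcting in the analysis still to come; it does not undermine the inhibitor results themselves.

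**What to change.** In the SAP for the overall main-plus-extension analysis:
1. Apply one treatment-emergent window to Part A, Part B and the extensions, namely the Part B rule of 7 days after the last study infusion.
2. Carry over the Part B provision that an inhibitor is treatment-emergent whenever it develops after the first study dose.
3. Date an inhibitor AE to the first positive sample, so that its onset does not depend on when the result or the confirmation arrived.
4. Re-derive the flag for Part A and report any event whose status differs from the earlier Part A report.

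The cost is a few lines of SAP text and a rerun of the AE flag; no new data are needed. The downside is that a few late, unrelated events may enter the tables and some Part A figures may differ slightly from those already reported. Step 4 makes any such difference visible.

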7.5.3.4 Inhibitor testing

Premise for inclusion **requires confirmed diagnosis of severe hemophilia A (<1% FVIII) and documentation of a (as of Amd 1)** negative test result of inhibitor at Baseline.

Blood samples for FVIII inhibitor testing will be taken at Screening (**PTPs and MTPs only**), Baseline, **at regularly scheduled intervals throughout the study, and at the (as of Amds 1 and 6)** final visit. The premise for inclusion of **PTPs and MTPs** in this study is the availability of a negative inhibitor **result (as of Amds 1 and 6)** as measured in the blood sample at Screening **and Baseline (as of Amd 7)**. A further sample will be taken at baseline before the first **infusion (as of Amd 1)**. If the inhibitor testing result changes from negative at screening

to positive at baseline, before the first *infusion (as of Amd 1)* of study medication, the subject must be withdrawn from the trial.

In Part B, the requirement for a FVIII inhibitor testing before study entry (as of Amd 1) is not applicable for PUPs but is applicable for MTPs (as of Amd 6). The absence of inhibitors will be assessed using central laboratory testing at Screening (<0.2 BU/mL), with confirmation using local laboratory testing at Baseline (<0.6 BU/mL) (as of Amd 7). After treatment is started (as of Amd 1), PUPs/MTPs must be tested for inhibitor development every 3-5 ED until 20 ED are accumulated (as of Amd 6), and at the final visit (50 ED) (as of Amd 7). Afterwards, blood samples for inhibitor testing and determination of FVIII:C trough level (>48 h after last FVIII treatment) are to be taken:

- ***every 6 months in the extension study until finalization of the study, and at the final visit (as of Amds 1 and 6).***

The laboratory analyses will be performed at central laboratories.

Investigators will be provided with a detailed laboratory manual and a copy of the individual results. Inhibitor testing will be done according to the Nijmegen modified Bethesda inhibitor assay ***at the central laboratory (as of Amd 1)***. A positive inhibitor testing is defined with a threshold of ≥ 0.6 BU in the central laboratory. Any positive test must be confirmed by a second ***plasma (as of Amd 1)*** sample ***and a determination of recovery should be performed. (as of Amd 6)***

For any subject confirmed positive for inhibitors, epitope mapping will be performed (see Section 7.6.1 for details). (as of Amd 4)

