8.3 Variables

Baseline

Demographic characteristics, including age, weight, height and race as well as previous exposure to FVIII will be presented for all treated subjects, in the form of summary statistics. Other baseline characteristics, including laboratory findings and vital signs, will be handled similarly.

Extent of Exposure

Extent of exposure to the study drug, including *treatment (as of Amd 1)* characteristics, will be documented in subject diaries and summarized for each subject receiving any amount of drug.

Safety

Safety data will be summarized for all subjects in the safety population. Laboratory findings, AEs, concomitant medications, and medical history data will be provided in subject listings.

Laboratory values and vital signs will be summarized. Individual listings of AEs [including AEs as reported, start, duration, severity, relation to study drug] will be provided. The incidence of treatment-emergent AEs will be summarized using the Medical Dictionary for Regulatory Affairs (MedDRA). *(some text deleted as of Amd 1)*

Inhibitor development, as measured by Nijmegen assay, will be summarized by time point and presented in subject listings. *The purpose of the listing is to delineate the clinical factors which may be positively associated with development of the inhibitor. (as of Amd 1)*

The frequency of subjects who develop positive inhibitor titers (Bethesda ≥ 0.6 BU) and *confirmed by repeat measurement (as of Amd 1)* will be presented by time point. *If the inhibitor value drops below 0.6 BU on repeat measure without intervention, the inhibitor will be determined as being transient. We will classify inhibitor patients as being either low titer or high titer based upon persistence of an inhibitor >5 BU. (as of Amd 1)* The rate of inhibitor development associated with BAY 81-8973 will be determined. Subjects with no inhibitors are required to have at least 50 ED to be counted in the denominator.

Efficacy

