Laboratory values and vital signs will be summarized. Individual listings of AEs [including AEs as reported, start, duration, severity, relation to study drug] will be provided. The incidence of treatment-emergent AEs will be summarized using the Medical Dictionary for Regulatory Affairs (MedDRA).

Inhibitor development, as measured by Nijmegen assay, will be summarized by time point and presented in subject listings. The purpose of the listing is to delineate the clinical factors which may be positively associated with development of the inhibitor. The frequency of subjects who develop positive inhibitor titers (Bethesda \geq 0.6 BU) and confirmed by repeat measurement will be presented by time point. If the inhibitor value drops below 0.6 BU on repeat measure without intervention, the inhibitor will be determined as being transient. We will classify inhibitor patients as being either low titer or high titer based upon persistence of an inhibitor >5 BU.

The rate of inhibitor development associated with BAY 81-8973 will be determined. Subjects with no inhibitors are required to have at least 50 ED to be counted in the denominator.

Efficacy

Efficacy data will be summarized for all subjects in the intent-to-treat (ITT) population. The primary efficacy variable will be the annualized number of total bleeds (sum of spontaneous bleeds and traumatic bleeds) within 48 hours after a prophylaxis infusion. Other variables summarized will be the physician's/subject's/parents' assessment of the response to treatment of bleeds (excellent, good, moderate, poor) and during surgeries. The number of treatments required to control bleeds, the proportion of prophylaxis infusions with less than expected therapeutic effect (LETE) (defined as a prophylaxis infusion followed by a bleed within 48 hours), annualized number of total bleeds (sum of spontaneous bleeds and trauma bleeds) during prophylaxis, factor VIII usage and recovery will be summarized. A detailed Statistical Analysis Plan will be provided.

13.1.2.11 Change 11

Section 5.1.1 Inclusion criteria

Original protocol

In order to be included in the study, subjects must ~~meet~~ all of the following criteria upon evaluation at the Screening or Baseline visit:

1. Male, aged ≤ 12 years
2. Severe hemophilia A defined as $< 1\%$ factor VIII concentration (FVIII:C) based on ~~medical records~~ and/or screening laboratory
3. ≥ 50 ED with any ~~high purity~~ FVIII;

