14.5 Laboratory evaluation for suspected inhibitor (as of Amd 1)

If an inhibitor is clinically suspected (a bleed that progresses or does not improve following appropriate therapy), the subject be managed according to local standard of care. The investigator should immediately notify the sponsor and obtain the following information and blood tests:

- *time and dose of last infusion*
- *infused product (if other than BAY 81-8973)*
- *blood for central laboratory*
 - *pre and post FVIII level/ Activated Partial Thromboplastine Time (aPTT)*

- *inhibitor to Factor VIII testing by the Nijmegen assay*

If inhibitor is confirmed, the subject may receive immune tolerance therapy using BAY 81-8973. (See section 6.1.4)

If an inhibitor is detected as part of scheduled testing, the investigator will be notified. A positive inhibitor test is defined with a threshold of ≥ 0.6 BU in the central laboratory. Any positive test must be confirmed by a second plasma sample. Pre and post infusion samples will be required for confirmation. (as of Amd 1)

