6.5 Additional analyses planned to be reported outside the main report	
7. Document history and changes in the planned statistical analysis	16
8. References	16

Statistical Analysis Plan

BAY 81-8973 / 13400

Abbreviations

AE	Adverse event
ANOVA	Analysis of variance
AUC	Area under the curve
BU	Bethesda unit
CL	clearance
C _{max}	maximum concentration
CS/ADJ	Chromogenic Substrate Assay Adjusted to Label Potency
CS/EP	Chromogenic Substrate Assay / Per European Pharmacopeia
dL	deciliter
DMC	Data Monitoring Committee
CRF	Case Report Form
eCRF	Electronic Case Report Form
ED	exposure day
EPD	Electronic Patient Diary
FVIII	Factor VIII
IU	International Unit
IVR	in vivo recovery
kg	kilogram
LLOQ	lower limit of quantification
ITT	Intent-to-treat
MedDRA	Medical Dictionary for Regulatory Activities
MRT	mean residence time
n/a	not applicable
PDD	Protocol Deviations Document
PPS	Per-Protocol Analysis Set
PTP	previously treated patient
PUP	previously untreated patient
QoL	quality of life
rFVII	recombinant Factor VIII
PP	Per-protocol
SAF	Safety Analysis Set
SAP	Statistical Analysis Plan
t _{1/2}	half-life
TLF	Tables, Listings, Figures
V_{ss}	steady state volume

1. Introduction

This statistical analysis plan (SAP) is based on Integrated Protocol, Version 3.0, dated 03 Sep 2012.

This protocol version is an integration of the original protocol and the following global amendments:

Original protocol, Version 1.4, 20 Sep 2010 Amendment 1 forming integrated protocol Version 2.0, 31 Mar 2011 Amendment 3 forming integrated protocol Version 3.0, 03 Sep 2012

This SAP describes the study objective, study design, analysis sets, all endpoints, and statistical analysis methods for main evaluation period of previously treated patients (PTPs) in study 13400. Complete details of Tables, Listing and Figures (TLFs) specifications as well as dataset details and data handling specifications will be provided in "TLF specifications" and "Analysis Datasets" documents which are an integral part of this SAP.

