6.4.3 Laboratory parameter

Laboratory values, incidence of high or low abnormal values, and changes from baseline will be summarized. In general only central laboratory values will be used for analysis. Where also local values are taken into consideration will be explicitly mentioned.

Two laboratory analytes, Anti HSP-70 and inhibitors, will be summarized in a listing that will include all values for those subjects with any positive result. Incidence of HSP-70 antibody formation and inhibitors will be assessed.

Inhibitor development, as measured by Bethesda assay will be summarized timepoint and presented in subject listings. The frequency of subjects who develop positive inhibitor titers (Bethesda ≥ 0.6 BU) as well as high titer (> 5.0 BU) will be presented. For the inhibitors as well as for the high titer inhibitors Kaplan Meier graphics for the occurrence will be provided.

A positive inhibitor testing is defined with a threshold of ≥ 0.6 BU in the central laboratory and a confirmation by

- a second plasma sample and a positive central testing or
- two consecutive local measurements (2^{nd} and 3^{rd} sample) with doubled threshold (Bethesda ≥ 1.2 BU).

In case a central value of the same samples used for local confirmation shows no inhibitor, the local confirmation is not valid.

High titer inhibitor needs not to be confirmed by a second high (> 5.0 BU) value, but the inhibitor itself needs a confirmation.

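### The Part A SAP tabulates inhibitors on a 0.6 BU threshold alone and omits the confirmation step that the protocol requires

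*SAP*

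**What the plan says.** **Part A SAP (v2.1, 19 Dec 2012), 6.4 Safety:** "The frequency of subjects who develop positive inhibitor titers (Bethesda ≥ 0.6 BU) will be presented". No repeat test or second sample is mentioned. Inhibitor results are also to be summarised by timepoint and given in subject listings.

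**Protocol 8.3, Safety:** the frequency to be presented is that of subjects at or above 0.6 BU and "confirmed by repeat measurement". A value that drops below 0.6 BU on repeat without intervention is classed as transient. Inhibitor-free subjects enter the denominator of the inhibitor rate only if they have at least 50 exposure days (ED).

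**Protocol 7.5.3.4:** "Any positive test must be confirmed by a second" plasma sample. **Protocol 14.5** repeats this: "Any positive test must be confirmed by a second plasma sample".

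**Part B SAP (v2.0), 6.4.3:** "A positive inhibitor testing is defined with a threshold of ≥ 0.6 BU in the central laboratory and a confirmation by" one of two routes. These are a second plasma sample that tests positive centrally, or two consecutive local values of at least 1.2 BU. The local route is void if a central value on the same samples shows no inhibitor.

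**The concern.** The protocol classes any inhibitor development as a serious adverse event (7.5.1.1), and Part A plans only 50 PTPs. In a group of that size a single subject moves the tabulated proportion by two percentage points, so the rule for who counts matters.

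The protocol does not treat an isolated low titre as an established inhibitor. Section 8.3 asks for a repeat and has a transient category, and 6.1.5 requires at least two positive titres plus decreased recovery for clinical relevance. The Part A SAP sentence makes none of these distinctions. A programmer who followed it literally would count a child whose retest was negative. The whole-study analysis could then combine a threshold-only count in Part A with a confirmed count in Part B.

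**Working it through.** **1. Was the confirmation clause in force when the SAP was written?** Amendment 1 (protocol v2.0, 31 Mar 2011) changed the 8.3 sentence to read "and confirmed by repeat measurement will be presented by time point". The Part A SAP's Introduction states: "This statistical analysis plan (SAP) is based on Integrated Protocol, Version 3.0, dated 03 Sep 2012". Version 3.0 integrates Amendment 1, so the clause was part of the protocol on which the SAP rests.

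**2. Is the omission flagged or repaired elsewhere?** Section 4.1 of the SAP flags its change to the total-bleeds definition as a change from the protocol. Section 6.4 flags nothing. The supplement of 18 Jul 2013 revises Sections 4.1, 4.4 and 6.2 only. Apart from the words on time point, the SAP sentence matches the text that Amendment 1 replaced. That suggests carry-over rather than a decision, though the documents do not say so.

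**3. What does one unconfirmed titre do to the table?** The inputs are 50 planned PTPs (25 aged 6–12 years plus 25 aged under 6; protocol 8.6) and one subject with a single value at or above 0.6 BU that is not confirmed. Intervals are exact (Clopper-Pearson). All 50 are assumed to reach 50 ED, so that both rules share a denominator. The sample size follows a guideline, so the plan has no precision figure to reproduce first.

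- SAP wording: 1/50 = 2.0%. The lower limit solves 1 − (1 − p)^50 = 0.025, giving 0.05%. The upper limit solves (1 − p)^50 + 50p(1 − p)^49 = 0.025, giving 10.6%.
- Protocol wording: 0/50 = 0%. The upper limit is 1 − 0.025^(1/50) = 7.1%.

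**4. Denominator.** Protocol 8.3 removes inhibitor-negative subjects with fewer than 50 ED. SAP 6.4 includes everyone who received any study drug and does not restate that rule. If any PTP falls short of 50 ED, the two rules also divide by different numbers.

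**5. How often would this happen?** The protocol synopsis schedules post-baseline tests at Months 1, 2 and 6, so 50 × 3 = 150 tests. With a false-positive rate f per test and independent tests, the chance of at least one false positive is 1 − (1 − f)^150. No document gives f. The values below are assumptions, shown only to display the range; the last column also assumes an independent retest with the same f, giving 1 − (1 − f²)^150.

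| Assumed f | Threshold only | With confirmation |
|---|---|---|
| 0.1% | 13.9% | 0.01% |
| 0.5% | 52.9% | 0.4% |
| 1% | 77.9% | 1.5% |
| 2% | 95.2% | 5.8% |

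The threshold-only column runs from 14% to 95% and follows the assumed f almost entirely, so it supports no statement of likelihood.

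**The case against.** - **The SAP is silent; it does not say that any single titre counts.** A reader might infer that it deliberately does, but the text does not go that far. The Part A SAP makes the TLF specifications and Analysis Datasets documents an integral part of the plan. They were not available for this review and could hold the confirmation step. The conflict in the SAP text stands; actual misreporting is not shown.
- **The sentence may be shorthand.** Part B SAP 6.4.3 uses nearly the same threshold-only sentence and then defines a positive separately. The Part A SAP could be relying on the protocol for that definition. This is plausible, but in Part A no definition follows and no cross-reference is given.
- **A false positive might seem likely.** The documents do not support that. They give no assay error rate, and the calculation treats repeated tests within a child as independent.
- **A positive that reverts is not necessarily an assay error.** Protocol 8.3 calls it a transient inhibitor, so such a case should be shown under that label, outside the confirmed frequency, and not discarded.
- **The consequence is limited.** The analysis is descriptive, listings would show a negative retest, and the error runs towards over-reporting a safety event. All of this stands, but the tabulated frequency would still differ from the protocol's.
- **Part A is already reported.** The Part B SAP's Introduction says that the 6-month PTP analysis is complete. A SAP edit cannot change that report. The live target is the whole-study analysis in protocol 8.5, which takes in all main and extension data.

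**Conclusion.** The Part A SAP's stated rule for inhibitor frequency conflicts with protocol 8.3, with the second-sample requirement in 7.5.3.4 and 14.5, and with the Part B SAP. Nothing in the available documents repairs or explains this. Confidence in the omission is high.

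Its size is one subject: 1/50 (2.0%, 95% CI 0.05% to 10.6%) in place of 0/50 (0% to 7.1%) for each unconfirmed titre that would otherwise stand alone. This rests on the planned 50 PTPs, all with at least 50 ED, and on the SAP being applied literally. It needs no assumption about assay error. No probability is attached. A reader might also infer that the completed Part A report contains a spurious inhibitor; the documents give no basis for that, and only a check of the rule used can settle it.

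**What to change.** In Part A SAP 6.4, and in the SAP for the final whole-study analysis:

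1. Count an inhibitor only if the titre is at least 0.6 BU in the central laboratory and confirmed by a repeat sample, as in protocol 8.3.
2. Tabulate or list separately, as transient or unconfirmed, positives that fall below 0.6 BU on repeat.
3. Apply protocol 8.3's 50-ED denominator rule.
4. State whether Part B's local-laboratory route (two consecutive values of at least 1.2 BU, void if the central value is negative) also applies to PTPs. Copying only the second-sample wording would leave the two parts different.

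Check which rule the completed Part A report used, and state it when those data enter the final analysis. If the TLF or dataset specifications already contain the confirmation step, cite it in the SAP.

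The cost is a small SAP edit and one check of the existing derivation. The repeat samples are already mandatory, so no new data collection is needed.
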